10.2 Adverse Events

A treatment-emergent Adverse Event (TEAE) is defined as an adverse event with an onset date that is after the first dose of study drug, and no more than 30 days after the last dose of study drug. Events where the onset date is the same as the study drug start date are assumed to be treatment-emergent, unless the study drug start time and the adverse event start time are collected, and the adverse event start time is prior to the study drug start time. If an incomplete onset date was collected for an adverse event, the event will be assumed to be treatment-emergent unless there is other evidence that confirms that the event was not treatment-emergent (e.g., the event end date was prior to the study drug start date).

AEs will be summarized and presented using primary MedDRA System Organ Classes (SOCs) and preferred terms (PTs) using MedDRA Version 27.1 or most up to date version. The actual version of the MedDRA coding dictionary used will be noted in the AE tables and in the clinical study report. Specific adverse events will be counted once for each subject for calculating percentages, unless stated otherwise. In addition, if the same adverse event occurs multiple times within a subject, the highest severity and level of relationship to investigational product will be reported.

10.2.1 Adverse Event Overview

An overview of TEAEs per 100 patient-years of study drug exposure will be presented for the following categories:

- Any TEAE
- Any TEAE related to study drug according to investigator assessment
- Any Severe TEAE
- Any Serious TEAE
- COVID-19 TEAE
- Any TEAE leading to discontinuation of study treatment
- Any TEAE Leading to Death
- All Deaths

The number of TEAEs reported, the total number of years of study drug exposure, and the TEAE rate per 100 patient-years will be presented. An overview of TEAE incidence rate per 100 patient-years of exposure will also be presented.

10.2.2 Treatment-Emergent Adverse Events by SOC and PT

TEAEs per 100 patient-years of study drug exposure will be summarized by SOC and PT. The following summaries of adverse events will be generated:

- All TEAEs
- Serious TEAEs
- Severe TEAEs
- TEAEs related to study treatment according to the investigator
- TEAEs leading to discontinuation of study treatment
- TEAE leading to death
- COVID-19 TEAE

TEAEs will be summarized by SOC and PT; by maximum relationship to study treatment as assessed by the investigator (e.g., reasonable possibility or no reasonable possibility) and SOC and PT; by maximum severity and SOC and PT.

10.2.3 Deaths, Serious Adverse Events, and Adverse Events Leading to Study Treatment Discontinuation

Treatment-emergent serious adverse events (SAEs), TEAEs leading to premature discontinuation of study treatment, and TEAEs leading to death will be summarized by SOC and PT.

Tabular listings will be provided for all deaths, all SAEs, TEAEs leading to death, TEAEs leading to premature discontinuation of study treatment.

10.2.4 Adverse Events of Special Interest

Adverse events of special interest will be summarized by SOC and PT and will be based on standardized or AbbVie-defined company MedDRA queries (SMQs or CMQs), or based on adjudication results. Adjudicated cardiovascular events will be summarized using the CAC adjudicated categories. Adverse events of special interest categories and detailed information about the search criteria are listed in [Table 4](#).

A summary of non-treatment-emergent malignancy events will also be presented.

Tabular listings of treatment-emergent adverse events of special interest will be provided.

An overview of AESIs per 100 patient-years of study exposure will be presented. The number of TEAEs reported, the total number of years of study drug exposure, and the TEAE rate per 100 patient-years will be presented. Additionally, an overview of AESIs Incidence rate per 100 patient-years of study drug exposure will be also presented.

Table 4. AESI for Upadacitinib with SMQs/CMQs/PTs Searches

AESI	Type of MedDRA Query	Broad or Narrow Search	SMQ/CMQ Search Criteria
Serious Infections	CMQ		"Infections" – Subset for SAEs
Opportunistic Infection excluding Tuberculosis and Herpes Zoster	CMQ		"Opportunistic Infection excluding Tuberculosis and Herpes Zoster"
Possible Malignancy	SMQ	Narrow	"Malignancies"
Malignancy	SMQ	Narrow	"Malignant tumours"
Non-Melanoma Skin Cancer (NMSC)	SMQ	Narrow	Skin Malignant tumours (Narrow SMQ) removing Melanoma CMQ
Malignancy excluding NMSC			"Malignant tumours" SMQ (Narrow) removing NMSC output
Lymphoma	SMQ	Broad	"Malignant Lymphomas"
Hepatic Disorder	SMQ	Narrow	"Drug Related Hepatic Disorders" comprehensive search
Adjudicated Gastrointestinal Perforations	Output from adjudication		
Anemia	CMQ		"Non-Hemolytic and Non-Aplastic Anemias"
Neutropenia	CMQ		"Hematological Toxicity – Neutropenia"
Lymphopenia	CMQ		"Hematological Toxicity – Lymphopenia"
Herpes Zoster	CMQ		"Herpes Zoster"
Renal Dysfunction	SMQ	Narrow	"Acute Renal Failure"
Active Tuberculosis	CMQ		"Active Tuberculosis"
Bone Fracture	CMQ		"Bone Fracture"
Serious Hypersensitivity Reaction	SMQ	Narrow	"Anaphylactic Reaction" (SMQ narrow) including "Angiodema" (SMQ Narrow) – subset to SAEs
Retinal Detachment	CMQ		"Retinal Detachment"
Acute Renal Failure	SMQ	Narrow	"Acute Renal Failure"

AESI	Type of MedDRA Query	Broad or Narrow Search	SMQ/CMQ Search Criteria
Adjudicated Cardiovascular Events	Output from CAC		
MACE*			
Cardiovascular Death			
Non-fatal Myocardial Infarction			
Non-fatal Stroke			
Undetermined/Unknown Cause of Deaths			
Other Cardiovascular events			
Adjudicated Thrombotic Events	Output From CAC		
Venous Thromboembolic Events**			
Deep Vein Thrombosis			
Pulmonary Embolism			
Other Venous Thrombosis			
Arterial Thromboembolic Events (non-cardiac, non-neurologic)			

CAC Cardiovascular Adjudication Committee; CMQ company MedDRA query; PT preferred term;
 SMQ standard MedDRA query

* MACE; Major Adverse Cardiovascular Events, defined as cardiovascular death, non fatal myocardial infarction and non fatal stroke.

** Venous thromboembolic events (VTE) include deep vein thrombosis (DVT) and pulmonary embolism (PE) (fatal and non fatal).

Additional AEs may be considered for summary based on recommendations from Clinical and Safety as deemed appropriate.

10.3 Analysis of Laboratory Data

Data collected from central and local laboratories, including additional laboratory testing due to an SAE, will be used in all analyses, except for period baseline where SAE-related laboratory assessments on or before the first dose of study drug will be excluded.

10.3.1 Variables and Units

Safety laboratory parameters to be summarized in this study are listed below. Laboratory parameters will be reported using the standard international (SI) units.

Table 5. List of Safety Laboratory Variables

Laboratory Variables
Hematology
Leukocytes (White Blood Cell Count)
Erythrocytes (Red Blood Cell Count)
Hemoglobin
Hematocrit
Platelets
Neutrophils
Basophils
Eosinophils
Lymphocytes
Monocytes
Erythrocytes Mean Corpuscular Volume
Reticulocytes/Erythrocytes

Laboratory Variables

Chemistry

Total Bilirubin
Alkaline Phosphatase (ALP)
Aspartate aminotransferase (AST)
Alanine aminotransferase (ALT)
Total Protein
Albumin
Glucose
Triglycerides
Blood Urea Nitrogen (BUN)
Creatinine
Uric acid
Sodium
Potassium
Calcium
Inorganic Phosphorus
Chloride
Bicarbonate
Cholesterol
LDL cholesterol
HDL cholesterol
LDL/HDL ratio
Cholesterol/HDL ratio

Urinalysis

Specific Gravity
pH

10.3.2 Assessment of Mean Change from Baseline in Clinical Laboratory Variables

For UPA reinitiation, each laboratory variable will be summarized for all time points (starting with visit at first dose of reinitiated upadacitinib) with the number of non-missing observations, mean and standard deviation, median, minimum and maximum.

Mean change from Original Baseline to each applicable post-baseline visit will be summarized for selected laboratory variables, with the number of observations, reinitiation baseline mean, and visit mean. The change from Original Baseline mean, standard error, and 95% confidence interval will be presented for the mean change from Original Baseline overall and for Study 1 and Study 2 subgroups.

No summary of laboratory data by visit will be provided for ALL UPA.

10.3.3 Assessment of Potentially Clinically Important Laboratory Values

The criteria for potentially clinically important laboratory values will be determined by CTCAE v4.03 criteria of Grade 3 or higher.

Laboratory abnormalities will be evaluated based on Potentially Clinically Important (PCI) criteria ([Appendix D](#)). For each laboratory PCI criterion, the number and percentage of subjects who have a laboratory value meeting CTCAE v4.03 criteria Grade 3 and 4 will be summarized. Listings will be provided to summarize subject-level laboratory data for subjects meeting PCI criteria. A listing of possible Hy's Law cases will be provided.

10.3.4 Assessment of Liver Elevations

According to FDA's Guidance for Industry "Drug-Induced Liver Injury: Premarketing clinical evaluation" (July 2009), when aminotransferase (AT) abnormalities indicating hepatocellular injury are accompanied by evidence of impaired hepatic function (Total bilirubin elevation $> 2 \times$ ULN), in the absence of evidence of biliary obstruction (i.e., significant elevation of ALP) or some other explanation of the injury (e.g., viral hepatitis, alcohol hepatitis), the combined finding (i.e., Hy's Law cases) represents a signal of a potential for the drug to cause severe DILI.

For the purpose of assessing for potential Hy's law cases, the frequencies and percentages of subjects with post baseline liver specific function test values that meet the following criteria of potential clinical interest will be summarized. Listings will be provided to

summarize subject-level laboratory data for subjects meeting liver elevations based on criteria specified below:

- $ALT \geq 3 \times ULN$
- $ALT \geq 5 \times ULN$
- $ALT \geq 10 \times ULN$
- $ALT \geq 20 \times ULN$
- $AST \geq 3 \times ULN$
- $AST \geq 5 \times ULN$
- $AST \geq 10 \times ULN$
- $AST \geq 20 \times ULN$
- $TBL \geq 2 \times ULN$
- Alkaline phosphatase $\geq 1.5 \times ULN$
- ALT and/or $AST \geq 3 \times ULN$ and $TBL \geq 1.5 \times ULN$
- ALT and/or $AST \geq 3 \times ULN$ and $TBL \geq 2 \times ULN$

For criteria involving multiple parameters, the values do not need to be concurrent to meet the defined criteria.

10.4 Analysis of Vital Signs

Vital sign measurements of systolic and diastolic blood pressure, pulse rate, respiratory rate, body temperature, and weight will be summarized.

For UPA reinitiation, each vital sign variable will be summarized for all visits (starting with visit at first dose of reinitiated upadacitinib) with the number of non-missing observations, mean and standard deviation, median, minimum and maximum. Mean change from Original Baseline to each applicable post-baseline visit will be summarized for each vital sign variable, with the number of observations, Original Baseline mean, and visit mean. The change from Original Baseline mean, standard error, and 95% confidence interval will be presented for the mean change from baseline.

No summary of vital sign data by visit will be provided for ALL UPA.

Vital sign variables will be evaluated based on potentially clinically important (PCI) criteria ([Appendix D](#)). For each vital sign PCI criterion, the number and percentage of subjects who have a vital sign value meeting the criteria will be summarized. Listings will be provided to summarize subject-level vital sign data for subjects meeting PCI criteria.

11.0 Other Analyses

Not Applicable.

12.0 Interim Analyses

Not Applicable.

13.0 Overall Type-I Error Control

There is no formal statistical testing in the Remission-Withdrawal study. Thus, no Type-I error control is planned in this study.

14.0 Version History

Table 6. SAP Version History Summary

Version	Date	Summary
1.0	08 August 2022	Original version
2.0	11 December 2024	
The following changes have been made:
 
 • Redefined safety analysis populations in Section 4.0 to collectively summarize patient safety of reinitiated upadacitinib after treatment withdrawal and to summarize patient safety of any upadacitinib in Study M19-944. • Updated treatment exposure duration in Section 6.0 to reflect the redefined safety analysis populations. • Moved description of intercurrent event handling to Section 8.0. • Removed estimand language in Section 9.0. • Streamlined safety analysis description in Section 10.0 for redefined safety analysis populations. • Aligned AESI categories in Section 10.2.4 to the most updated upadacitinib PSSAP (Version 8.0). • Removed COVID-19 or geo-political conflict language in Section 5.0, Section 9.2 and Section 9.3, and NRI-MI in Appendix as they are no longer applicable.

Appendix B. Protocol Deviations

Protocol deviations include eligibility criteria violations, receipt of wrong treatment or incorrect dose of study treatment, development of withdrawal criteria without being withdrawn, and use of excluded concomitant medications. A listing of subjects with protocol deviations will be provided.

For each of the following protocol deviation categories and across all categories, the number and percentage of randomized subjects with at least one protocol deviation will be summarized overall and by treatment group:

- Subject entered into the study even though did not satisfy entry criteria;
- Subject developed withdrawal criteria during the study but was not withdrawn;
- Subject received wrong treatment or incorrect dose of study treatment;
- Subject took excluded concomitant medication.

Appendix C. EAER and Normal Approximation Based 95% Confidence Interval

Assume the occurrence of TEAE of special interest follows a Poisson distribution and let λ denote the rate of occurrence of TEAE under the total exposure time for a treatment group. Let n be the number of AEs reported in Any upadacitinib 15 mg QD group. Let T be the total time exposed to study drug summed across all treated subjects in Any upadacitinib 15 mg QD group. Under the assumption that n follow Poisson distribution with parameters λT , the $\hat{\lambda} = n/T$.

Using normal approximation, the 95% confidence interval can be calculated by (Liu GF et al. 2006.¹⁰):

$$\hat{\lambda} \pm Z_{\alpha/2} \hat{\sigma}$$

Where $\hat{\sigma} = \sqrt{\frac{n}{T^2}}$

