10.0 Safety Analyses

10.1 General Considerations

Safety data will be summarized for the safety populations defined in Section 4.0.

The safety analyses will include reporting of adverse events (AEs), adverse events of special interest (AESI), laboratory, and vital sign measurements. Exposure-adjusted event rate (EAER) over 100 patient-years for subjects with treatment-emergent adverse events (TEAEs) will be provided to adjust for potentially different follow-up time between subjects. For the purpose of event rate calculation, the numerator will be the total number of AEs reported for the event (i.e., a subject can contribute more than one event to the numerator) and the denominator will be the total exposure time among subjects. The number of AEs reported (numerator), the total number of years of exposure (denominator calculated as total number of days of exposure for all treated subjects divided by 365.25), and the exposure-adjusted AE event rate per 100 patient-years calculated as $(\text{numerator} / \text{denominator}) \cdot 100$ will be presented.

In addition, exposure-adjusted incidence rate (EAIR) will be provided for AE Overview and Adverse Events of Special Interest (AESI) as deemed appropriate for long-term analysis. For the purpose of incidence rate calculation, the numerator will be the number

of subjects with AE reported for the event (i.e., a subject can contribute at most once to the numerator) and the denominator will be the total exposure time among subjects in the treatment group and at risk of an initial occurrence of the event, i.e., for subjects with no event, it is the total exposure time under the treatment group; for subjects with an event, it is the exposure time to the first event. The numerator, denominator (calculated as total number of days exposed to study drug for all treated subjects divided by 365.25), and the exposure-adjusted incidence rate per 100 patient-years calculated as $([\text{numerator}/\text{denominator}]) \cdot 100$ will be presented for each treatment group.

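### SAP Appendix C gives the all-events rate a pure Poisson standard error, so its 95% interval is too narrow if events cluster within subjects; the documents do not fix by how much

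*SAP*

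**What the plan says.** SAP Section 10.1 plans two rates per 100 patient-years. For the EAER, "a subject can contribute more than one event to the numerator". For the exposure-adjusted incidence rate (EAIR), "a subject can contribute at most once to the numerator". Section 10.2.4 plans both for adverse events of special interest (AESIs): besides the event rate, "an overview of AESIs Incidence rate per 100 patient-years of study drug exposure will be also presented".

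Appendix C gives an interval for the EAER only. Its steps are:

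- Model: "Assume the occurrence of TEAE of special interest follows a Poisson distribution".
- Numerator: "Let n be the number of AEs reported in Any upadacitinib 15 mg QD group".
- Denominator: "Let T be the total time exposed to study drug summed across all treated subjects".
- Distribution: "Under the assumption that n follow Poisson distribution with parameters λT", so λ̂ = n/T.
- Interval: "Using normal approximation, the 95% confidence interval can be calculated by" λ̂ ± z·σ̂, with σ̂ = √(n/T²) = √n/T.

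The SAP offers no over-dispersion factor, subject-level variance, negative binomial model or bootstrap as an alternative. Sections 10.1, 10.2.1 and 10.2.4 list counts, exposure and rates without mentioning an interval for adverse-event rates, so Appendix C is the only specification. Section 13.0 states that there is no formal testing.

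**The concern.** The numerator and the variance rest on different pictures of the data. The numerator admits several events from one person. The variance treats the n events as independent. It fails if one event makes another more likely in the same subject, or if subjects are regarded as draws from a population whose rates vary. In either case Var(n) is larger than λT and the interval claims more precision than the data carry.

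Repeats are plausible from the documents. SAP Table 4 lists anemia, neutropenia, lymphopenia, hepatic disorder and serious infections. Protocol Section 6.2 provides for interruption and restart of study drug and, for its supplemental case report forms, counts a laboratory abnormality that returns after normalising as a new event. SAP Section 6.0 tabulates exposure up to four years and beyond, which gives time for recurrence.

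At stake is the stated uncertainty of AESI rates in the ALL UPA population, which SAP Section 4.0 uses for the overall safety picture. With no tests planned, an interval, if shown, is the main expression of that uncertainty.

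**Working it through.** **Inputs.** From the documents: 95% two-sided (z = 1.960), σ̂ = √n/T, and planned enrolment 386 + 304 = 690. Assumed: all 690 enter ALL UPA; 1.9 years of exposure each; the event rates; the dispersion. For orientation on exposure, the protocol synopsis gives 90 or 104 weeks of upadacitinib in Study 1 and 52 or 104 in Study 2. With 1:1 allocation and full completion the mean is (386 × 97 + 304 × 78)/690 = 88.6 weeks, or 1.70 years, before any re-treatment or extension.

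**1. The formula under its own assumption.** With n truly Poisson, simulated coverage is 94.8% to 95.0% for 39 to 2,622 expected events. The nominal level is reproduced.

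**2. Variance under clustering.** Let subject i have rate λgᵢ, with gᵢ gamma-distributed, mean 1 and variance v. Then Var(nᵢ) = λtᵢ + vλ²tᵢ². With equal exposure t, Var(n) = λT(1 + vλt). The variance inflation factor is VIF = 1 + vλt, the standard error is too small by √VIF, and coverage ≈ 2Φ(1.96/√VIF) − 1.

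Example: λ = 0.10 per year, t = 1.9 and v = 1 give VIF = 1 + 0.19 = 1.19 and coverage of 92.8%.

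| Events per 100 PY | VIF, v = 1 | Simulated coverage | VIF, v = 2 | Simulated coverage |
|---|---|---|---|---|
| 3 | 1.06 | 94.2% | 1.11 | 93.3% |
| 10 | 1.19 | 92.8% | 1.38 | 90.4% |
| 50 | 1.95 | 83.7% | 2.90 | 74.5% |
| 200 | 4.80 | 62.6% | 8.60 | 49.3% |

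The last two rows describe frequent, recurring events, not rare AESIs. The excess VIF − 1 is proportional to t, so longer exposure raises it.

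**3. Clustering expressed as repeats per affected subject.** If affected subjects have a geometric number of events with mean μ, VIF = E[m²]/E[m] = 2μ − 1.

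- μ = 1: VIF 1.0, coverage 95.0%
- μ = 1.1: VIF 1.2, coverage 92.6%
- μ = 1.5: VIF 2.0, coverage 83.4%
- μ = 2: VIF 3.0, coverage 74.2%

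**4. Subject-level variance.** Take σ̂² = Σ(nᵢ − λ̂tᵢ)²/T². In simulation with v = 1 and the four rates above, coverage is 94.4% to 94.9%. Mean half-widths per 100 PY, Appendix C against subject-level, are 0.93 and 0.96 at a rate of 3; 1.71 and 1.86 at 10; 3.8 and 5.3 at 50; 7.7 and 16.7 at 200. With v = 0 the two agree (1.71 and 1.71 at a rate of 10).

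**5. Events that never repeat.** With nᵢ equal to 0 or 1 and equal exposure, Σ(nᵢ − λ̂tᵢ)² = n(1 − n/N). For n = 39 and N = 690 this is 39 × 0.943 = 36.8, so the standard error changes by about 3%, downwards.

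**6. Very low counts.** With a true Poisson count the normal approximation covers 86.8% at 5 expected events and 77.7% at 1.5. No clustering is involved here.

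**The case against.** The case for leaving Appendix C alone has real substance.

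- The assumption is stated openly, and the interval is descriptive. No decision, test or comparison between the two indications depends on it. This stands, and limits the harm.
- Appendix C covers AESIs, many of which can hardly recur on treatment. Under Protocol Sections 5.5 and 6.2, malignancy (with stated exceptions), active tuberculosis, gastrointestinal perforation and confirmed thrombosis end study drug. Under Section 6.1, laboratory abnormalities count as adverse events only in defined circumstances. This stands for those AESIs, but not for serious infections or recurrent cytopenias.
- The EAIR is reported beside the EAER, so heavy repetition would be visible. True, but the EAIR is a different quantity and does not correct the EAER interval.

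Some stronger readings are also tempting. A reader might infer that unequal rates among subjects are enough to break the Poisson variance. They are not: independent Poisson counts with different fixed rates still sum to a Poisson count. Excess variance needs dependence within a subject, or subjects viewed as a sample from a population with varying rates. A reader might also take coverage of 74% to 83% as what to expect. That requires a VIF of 2 to 3. At 0.2 events per subject, a VIF of 2 needs v = 5 (1 + 0.2 × 5), far above the 1 to 2 used here, and nothing in the documents supports it.

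**Conclusion.** The point holds in conditional form. The direction is clear: positive clustering within subjects makes the Appendix C interval too narrow, and the SAP has no provision for it. The size cannot be read from the documents. Under the assumptions above, the loss is about 1 to 2 percentage points of coverage at 3 events per 100 patient-years and about 2 to 5 at 10. It becomes large only for events that recur often in the same people, or if the formula were carried over to all treatment-emergent events, which Appendix C does not propose. For events that occur once per subject it is negligible.

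The documents do not support a claim that any safety conclusion, type I error rate or efficacy result is compromised. This concerns the accuracy of descriptive error bars.

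**What to change.** In Appendix C keep λ̂ = n/T and replace the variance with

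σ̂² = Σᵢ (nᵢ − λ̂tᵢ)² / T²,

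summed over all treated subjects, including those with no event, where nᵢ and tᵢ are a subject's event count and exposure. If the formula is kept as it is, Appendix C should at least say that the interval treats repeat events in one subject as independent. The EAIR needs no matching edit, since the SAP specifies no interval for it.

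The cost is one formula and about one line of code. The subject-level counts and exposure already exist and the point estimates do not change. Some intervals will be wider. The change does not repair the normal approximation at very low counts: with n = 0, for example, both formulas give an interval of zero width. That needs its own remedy.
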